### D.2. Data Analysis

**Primary Objective:** Our primary objective is to determine the completion rate for patients enrolling in this study. Patients who complete the dyspnea NRS on day 72 will be counted as successes. Dropouts are defined as subjects who do not complete the dyspnea NRS on day 7 +/- 2, and will be counted as failures toward the feasibility outcome. We will declare the study as feasible if we observe at least 20 successes, based on a recent review of Supportive Oncology studies in our department in which we found that approximately 50% patients completed their interventional clinical trial.

**Objective #2.** We will test our hypothesis that 4 days of dexamethasone will improve dyspnea, respiratory function and quality of life for cancer patients using paired t-tests.

**Objective #3.** We will test our hypothesis that 7 days of dexamethasone will improve dyspnea, respiratory function and quality of life for cancer patients using paired t-tests. A sample size of 20 per arm will allow us to detect an effect size of 0.9 in the change of dyspnea NRS between baseline and day 7 with an 80% power and an alpha of 5%, assuming a standard deviation of 2.

**Objective #4.** We will test our hypothesis that dexamethasone will improve dyspnea, respiratory function and quality of life for cancer patients compared to placebo using two-sample t-tests on the differences between baseline and 4 and 7 days for each outcome measure.

**Objective #5.** We will test our hypothesis that increased dose results in better outcomes by comparing the first 7 days of treatment arm to the last seven days of the placebo arm. We will use two-sample t-tests on the differences between baseline (day 0 for treatment arm, day 7 for placebo arm) and 7 days later (day 7 for treatment arm, day 14 for placebo arm).

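### Objectives #2, #3 and #5 are worded as tests of a drug effect and a dose effect that their comparisons cannot isolate; drug claims should rest on Objective #4, and #5 should carry no dose conclusion

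*Combined protocol and SAP*

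**What the plan says.** Section D.2 assigns these tests:

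- **Objective #2:** "4 days of dexamethasone will improve dyspnea, respiratory function and quality of life for cancer patients using paired t-tests".
- **Objective #3:** "7 days of dexamethasone will improve dyspnea, respiratory function and quality of life for cancer patients using paired t-tests". A power statement follows: "A sample size of 20 per arm will allow us to detect an effect size of 0.9 in the change of dyspnea NRS", with 80% power, 5% alpha and an SD of 2.
- **Objective #4:** dexamethasone "compared to placebo using two-sample t-tests on the differences between baseline and 4 and 7 days for each outcome measure". This is the only randomised, concurrent, blinded contrast among these objectives.
- **Objective #5:** "We will test our hypothesis that increased dose results in better outcomes by comparing the first 7 days of treatment arm" with the last seven days of the placebo arm, by two-sample t-tests on change from different baselines: "day 0 for treatment arm, day 7 for placebo arm".

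A.2 and A.3 describe #2 and #3 as comparisons of baseline with a later day, but their working hypotheses say that the drug improves outcomes. A.5 states a dose hypothesis. C.1 calls #5 exploratory and gives the study's main goal as estimating the effect size in both arms to inform a confirmatory trial. C.7 calls the whole study exploratory. The only decision rule is for feasibility: "We will declare the study as feasible if we observe at least 20 successes". No section says that conclusions about the drug rest on Objective #4.

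**The concern.** A paired t-test asks whether the mean changed in one group. It does not ask why. Patients enter with average dyspnea above 3/10 (C.2), so some improvement could come from regression to the mean, and placebo response and natural course add to it. A significant paired test would support the hypothesis as D.2 words it whether or not the drug did anything.

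Objective #5 uses the two randomised arms but compares different weeks of the study. The higher-dose week is blinded and starts at study entry. The lower-dose week is open label, starts from a new baseline after a week of placebo, and includes only patients still on study. Any difference mixes dose with these four factors.

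What is at stake is the inference carried forward. C.1 says the results are to inform a larger trial, and a change credited to the drug or to the higher dose could enter that trial's design as a drug or dose effect.

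**Working it through.** **1. The plan's own figure.** D.2 prints an effect size of 0.9 under #3, with 20 per arm, 80% power and SD 2. Sidedness and units are not stated; I take two-sided 5% and use the noncentral t distribution.

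| Reading of 0.9 | Power |
|---|---|
| Two-sample, 20 per arm, 0.9 SD (1.8 points) | 79.2% |
| Paired, n=20, 0.9 SD | 96.8% |
| Paired, n=20, 0.9 points (0.45 SD) | 48.0% |
| Two-sample, 20 per arm, 0.9 points | 28.4% |

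Only the first reading fits. The sentence stands under the paired objective but matches the between-arm test of Objective #4, so the plan may already have been sized for that contrast.

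**2. Objectives #2 and #3 with no drug effect.** Let m be the mean non-drug improvement in points. The paired statistic has noncentrality m√n/SD on n−1 degrees of freedom. For m=1, SD 2, n=20 this is 1×√20/2 = 2.24. Inputs:

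- SD 2 is from D.2. SD 3 is an assumption.
- m = 0.5 to 1.0 is an assumption.
- n=20 is full retention. n=10 follows from the completion rate that D.2 cites ("approximately 50% patients completed their interventional clinical trial"): 40 × 0.5 = 20, split equally.

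Chance of a significant paired test:

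| | m=0 | m=0.5 | m=1.0 |
|---|---|---|---|
| SD 2, n=20 | 5% | 19% | 56% |
| SD 2, n=10 | 5% | 11% | 29% |
| SD 3, n=20 | 5% | 11% | 29% |
| SD 3, n=10 | 5% | 8% | 16% |

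In Objective #4 the same m occurs in both arms and cancels (m − m = 0), so that test stays at 5% in every cell. Simulation with 100,000 trials per cell gave 4.9% to 5.1%.

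**3. The preliminary data in B.5.** At day 4 the printed change was −2 on dexamethasone and −1 on placebo, with between-arm P = 0.31. This shows qualitatively how a within-arm change can look like benefit when the between-arm contrast does not establish one. It cannot supply m, because the statistic and brackets are unlabelled. The printed placebo change is 0 at days 8, 15 and 22, so for #3 the non-drug change may be nil.

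**4. Objective #5, side by side.**

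| | Dexamethasone arm | Placebo arm |
|---|---|---|
| Days compared | 0 to 7 | 7 to 14 |
| Baseline | Study entry | After 7 days of placebo |
| Patient knows drug is active | No | Yes |
| Values needed | Day 0 and day 7 | Day 7 and day 14 |

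Regression to the mean after the entry threshold falls mainly on the dexamethasone arm's day-0 baseline. Open-label expectation falls only on the placebo arm's week. These can push in opposite directions, so I give no error rate for #5. With 20 of 40 patients completing day 7, split equally, it compares about 10 dexamethasone patients with at most about 10 placebo patients, since the latter also need a day-14 value.

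**The case against.** The strongest reply is that the plan already keeps the questions apart. A.2 and A.3 ask about change from baseline, which a paired t-test answers, and only Objective #4 is stated as a comparison with placebo. If the mean really falls by a point, rejecting a null of zero change is correct. #5 is labelled exploratory, the study is a pilot on a convenience sample, and no decision depends on #2, #3 or #5. The non-drug change is assumed. B.5 comes from a fatigue trial with a different regimen and shows a non-zero placebo change at only one of four time points. Entry uses a past-week average with a low threshold, which limits regression to the mean. No section says that the original assignment is revealed at day 7, so assessors may remain blind to arm.

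Much of this stands, and it lowers the severity. The rates above are illustrative, and they count as false positives only against the causal hypothesis. But that is the hypothesis D.2 says it will test. An exploratory label does not separate dose from period, baseline and attrition. Even if assessors stay blind to arm, patients in the second week know they are taking active drug, and the main outcomes are self-reported.

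**Conclusion.** The concern holds. As worded, D.2 would let a significant result in #2, #3 or #5 support a drug or dose hypothesis that the comparison cannot carry, although the randomised contrast that can address the drug hypothesis is already planned as Objective #4. The logical point is certain and does not depend on the size of m. The 8% to 56% range rests on an assumed non-drug change of 0.5 to 1.0 point, SD 2 or 3, and 10 or 20 patients; the true change could lie outside that range, and at zero there is no inflation. For #5 neither the size nor the direction of bias can be stated. This should be fixed, but at the low end of that grade: the primary objective is feasibility and no decision rule uses these tests.

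**What to change.** 1. **Objectives #2 and #3 in D.2.** Report the within-arm mean change with a 95% confidence interval for both arms; C.1 wants the effect size in both, while #2 and #3 name only dexamethasone. Add: *Within-arm changes are descriptive; any claim that dexamethasone improves an outcome rests on the randomised day-4 and day-7 contrasts of Objective #4.*
2. **Objective #5.** Report the two 7-day changes side by side with confidence intervals, as an exploratory estimate. State that this is not a concurrent randomised dose comparison, that it is confounded with period, blinding, baseline and attrition, and that no dose conclusion will be drawn.
3. **Section 1.0.** Align the working hypotheses in A.2, A.3 and A.5. As a side item, reconcile A.4, which omits quality of life, with D.2 Objective #4, which tests it.

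This needs text edits only: no new data and no change to treatment. The cost is precision. At 80% power the detectable effect is:

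| | Within-arm | Between-arm |
|---|---|---|
| 20 per arm | 0.66 SD | 0.91 SD |
| 10 per arm | 1.00 SD | 1.32 SD |

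At 20 per arm that is 1.3 against 1.8 points at SD 2, and 2.0 against 2.7 at SD 3. The 95% half-widths at SD 2 are 0.94 points within-arm and 1.28 between-arm at 20 per arm, and 1.43 and 1.88 at 10 per arm. The dose claim is given up; the open-label phase keeps its other purpose in C.1, giving every patient a chance to try the drug.

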## 5.0 Data Confidentiality Procedures

Health information will be protected and we will maintain the confidentiality of the data obtained from the patient's chart.

**Collection of identifiers:** We will collect and securely store patients' identifiers (including name, medical record number and demographic specifications). Each patient will be assigned a study number that will be the only identifier to figure in the analytical file and personal data will not be disclosed in any form. The key linking these numbers will be retained in a securely locked file by the investigator.

**Data Storage:** Protection of electronic and paper records will be guaranteed. All electronic records will be stored on password-protected institution computers behind the institution firewall. Any paper records will be classified and stored in locked files inside a locked office.

**Training of personnel:** Only MDACC personnel trained in maintaining confidentiality, the principle investigators and co-investigators, will have access to study records.

**Data sharing:** Study data will not be shared with any individuals or entities. The data will be kept by the principle investigator in a locked file cabinet.

**Final disposition of study records:** These data will be used only for this research study data files will be destroyed 5 years after publication of the findings.

